Clinical chemistry (including triglycerides and HDL-C)	X		X		X			X			X	X				X	X	Section 8.3.4 Fasting sample not required for Day -2 and Day 26
Coagulation (INR, PT and aPTT)	X																	Section 8.3.4
Serology (HIV I and II, HAV, HbsAg and HCV antibody, tuberculosis)	X																	Section 8.3.4
HbA1c	X																	Section 8.3.4
Pregnancy test (hCG)	X																X	Section 8.3.4. Females only

Visit	1	2	Visit 3 a						Washout (3 weeks) b	4	Visit 5 a						6	Comments
Phase	Screening	Outpatient visit	Residency in Unit a							Outpatient visit	Residency in Unit 2 a						Final/ET visit c	
Timing	≤ 14 days before start of IMP d	DAY														Follow-up 30 +/- 4 days after last dose of IMP		
		-4	-2	-1	1	2	3	4		24 (-4)	26 (-2)	27 (-1)	28 (1)	29 (2)	30 (3)	31 (4)		
TNFα j							X								X		
 
• Pre-dose
 
• Post-dose 1, 2, 4, 8, 12, 24 hoursk
 
• Section 8.2.4
 
	
PK (AZD9567)							X	X							X	X	
 
• Pre-dose
 
• Post-dose 0.25, 0.5, 1, 1.5, 2, 3, 4, 6, 8, 12, 24, 30 hoursk
 
• Section 8.6.1
 
	
PK (prednisolone)							X	X							X	X	
 
• Pre-dose
 
• Post-dose 0.25, 0.5, 1, 1.5, 2, 3, 4, 6, 8, 12, 24, 30 hoursk
 
• Section 8.6.1
 
	
Genetic research			X														Section 8.8 and Appendix D	

Visit	1	2	Visit 3 a						Washout (3 weeks) b	4	Visit 5 a						6	Comments
Phase	Screening	Outpatient visit	Residency in Unit a							Outpatient visit	Residency in Unit 2 a						Final/ET visit c	
Timing	≤ 14 days before start of IMP d	DAY														Follow-up 30 +/- 4 days after last dose of IMP		
		-4	-2	-1	1	2	3	4		24 (-4)	26 (-2)	27 (-1)	28 (1)	29 (2)	30 (3)	31 (4)		
MMTT				X				X				X				X	A standardised mixed meal will be administered around 0700 after an overnight fast. Blood samples to be taken 15 mins pre- and 10, 20, 30, 60, 75, 120, 180, 240 min post-mixed meal intake (see Section 5.3.1) for analysis of plasma glucose, insulin, C-peptide, GLP-1, GIP, glucagon and FFAs, see Sections 1.3.1, and 8.2.2	
Serum cortisol				X			X	X			X			X	X	X	Sample to be taken at 0800 	
CCI				X			X	X			X			X	X	X	Sample to be taken at 0800 	

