### 4.3 Justification for Dose

The most common prednisolone dosage to treat chronic inflammation is 5 – 60 mg/day, tapered to the minimally effective dose in order to impact disease activity while avoiding systemic adverse effects, including loss of glycemic control (British National Formulary (BNF)).

In this study, prednisolone doses of 5 mg, 20 mg, and 40 mg are selected as low to moderate clinically relevant doses spanning the range of therapeutic doses to relatively situate AZD9567 in terms of effects on glycemic control.

For meaningful assessment of differentiation, it is necessary to compare AZD9567 and prednisolone at doses with equal anti-inflammatory effect. In two recent dose escalation studies in healthy volunteers (D6470C00001 and D6470C00002), AZD9567 and prednisolone were evaluated with respect to anti-inflammatory biomarker effect, using inhibition of the cytokine TNF $\alpha$  from the immune cells, over 24 hours, following LPS stimulation in whole blood.

TNF $\alpha$  was inhibited by both AZD9567 and prednisolone in an exposure-dependent manner. A PK-PD modelling approach was used to establish dose–exposure–response relationships of TNF $\alpha$  for both compounds. Using these relationships, the dose AZD9567 that would produce the same level of TNF $\alpha$  inhibition as a given dose of prednisolone was predicted. A comparison of the dose-response curves enabled estimation of an equipotency relationship. Specifically, 20 mg prednisolone was estimated to be equipotent to 40 mg AZD9567 (95% CI: 29 – 54 mg), and 40 mg prednisolone was predicted to be equipotent to 72 mg AZD9567 (95% CI: 52 – 99) (Almquist et al 2020).

The validity of the equipotency analysis is supported by study D6470C00003 in patients with active RA despite stable treatment with conventional disease-modifying anti-rheumatic drugs,

where 40 mg AZD9567 resulted in a similar profile in term of efficacy effects to prednisolone 20 mg following 14 days of once daily dosing.

When comparing the effect of AZD9567 and prednisolone on glycemetic control in healthy volunteers, it was evident that the effect of AZD9567 at doses up to 80 mg on plasma glucose AUC(0–4h) after an OGTT were similar to those observed with 5 mg prednisolone.

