### **9.4.2.2 Secondary Endpoint(s)**

Mean daily glucose as measured by CGM will be evaluated as a secondary endpoint.

The mean daily glucose will be analysed using an MMRM analysis with baseline as covariate. Treatment, period, and sequence will be included as fixed effects, participant within sequence as random effect, and day as repeated measure. Models will be run separately for each cohort.

Similar analyses will be performed for the rise in mean daily glucose over 24-hour periods.

The secondary endpoints (insulin, glucagon, GLP-1, GIP), changes in FFAs during MMTT, C-peptide, 24-hour U-Na and U-K excretion and the ratio between them,  $\Delta I_{10}/\Delta G_{10}$ ,  $\Delta I_{30}/\Delta G_{30}$ ,  $\Delta C_{10}/\Delta G_{10}$ ,  $\Delta C_{30}/\Delta G_{30}$  and C-peptide will be summarised and analysed by means of a linear model or a mixed model for repeated measurements.

LPS-stimulated whole blood TNF $\alpha$  levels will be evaluated as a secondary endpoint for participants in Cohort 1 and Cohort 2 (high and low dose comparison). For TNF $\alpha$  profiles, the AUC will be estimated and the measurements at the sampling points will be summarised. Descriptive statistics will be tabulated both for the AUC and individual measurement points and treatments comparison will be conducted with ANOVA. Models will be run separately for each cohort.

Further details on statistical analyses will be provided in the SAP.

Descriptive statistics and graphical presentations will be presented as appropriate.

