4.12.2 Pharmacodynamics

All the models presented in this section will be analysed with unstructured covariance structure used for the within-participant errors. In the case of a model which does not converge, the analysis will be performed with a Toeplitz covariance structure and, in case of non-convergence, it will be performed with a compound symmetry structure.

Primary endpoint

The primary endpoint is the change in glucose AUC(0-4) and will be summarised by timepoint (baseline and Day 4) and by each cohort. The comparison of the change in glucose AUC(0-4) (where change from baseline in glucose AUC is assumed to be normally distributed) between the two treatments administered within each cohort after a standardised MMTT will be performed by means of two linear mixed effects models, with an unstructured covariance structure, with treatment, period and sequence as fixed effects, participant within sequence as random effect and baseline as covariate.

Two models will be run separately for each cohort:

1. In the first model, the dependent variable will be the change from baseline in AUC(0-4) whereas the AUC(0-4) on Day -1 will be included as a covariate. The treatment effects will be estimated by the Least Square means (LS means) and their 95% CIs and the difference between the two treatments by the difference in LS means with its 95% CI.

2. The second model will involve the following three steps:

a) Log-transformation of the AUC(0-4):

First, the AUC(0-4) in Day -1 and the AUC(0-4) in Day 4 will be log-transformed. The log-transformed AUC(0-4) in Day -1 will then be subtracted from the log-transformed AUC(0-4) in Day 4 to calculate the change in AUC (0-4) in log units.

b) Execution of the model:

The model will include the change in AUC (0-4) in log units as a dependent variable and the log-transformed AUC(0-4) in Day -1 as covariate.

c) Back-transformation of the results from the model:

The results from the execution of the model will be back transformed to the original scale after an exponentiation of the means and CIs estimated by the model to obtain the percentage geometric LS means of the treatments and their percentage SEs. The LS mean difference and its CI between the two treatments will also be back-transformed to yield the percentage geometric mean ratio between the two treatments with its 95% CI at Day 4.

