The same steps i) to iii) accordingly to timepoints 10 and 30, will be performed for $\Delta C_{10} / \Delta G_{10}$, $\Delta I_{30} / \Delta G_{30}$, and $\Delta C_{30} / \Delta G_{30}$.

The comparison of the effect of the two treatments on the change in $\Delta I_{10} / \Delta G_{10}$ and $\Delta I_{30} / \Delta G_{30}$, between Days -1 and 4 will be performed by the same model as that for the comparison of the primary endpoint.

The following comparison will be performed for the change from baseline and the percent change from changes from baseline at Day 4 at 10 and 30 minutes:

- 72 mg AZD9567 versus 40 mg prednisolone (Cohort 1)
- 40 mg AZD9567 versus 20 mg prednisolone (Cohort 2)
- placebo versus 5 mg prednisolone (Cohort 3).

The previous analyses will be repeated for the comparison of the effect of the two treatments on the change in $\Delta C_{10} / \Delta G_{10}$, $\Delta C_{30} / \Delta G_{30}$ using C-peptide instead of insulin in the calculation of these ratios.

HOMA-IR and HOMA-S

A summary of the baseline HOMA-IR and HOMA-S and at Day 4 as well as change from baseline, will be provided by treatment.

24-hour U-Na and U-K

The 24-hour Na and K concentration and its ratio (Na/K) in urine will be analysed as the primary endpoint.

The following comparisons will be performed for the change and percentage change from baseline at 0-24 hours on Day 3:

- 72 mg AZD9567 versus 40 mg prednisolone (Cohort 1)
- 40 mg AZD9567 versus 20 mg prednisolone (Cohort 2)
- placebo versus 5 mg prednisolone (Cohort 3).

TNF α concentrations

Descriptive statistics will be tabulated for the individual measurement points of the LPS-stimulated TNF α levels.

An ANOVA model with treatment, sequence and subject as random effect will be run separately for each cohort (Cohort 1 and Cohort 2) for the comparisons of the treatments at Day 3.

A scatter plot of individual plasma concentrations of AZD9567 (nmol/L) in a log scale on the X axis versus individual LPS-Stimulated TNF α Levels (ng/L) in log scale on the Y axis will be created.

CCI

[Redacted content]

CCI

CONFIDENTIAL

Project Document Version No. Final 2.0

Project Document Effective Date: <Date of last signature>

CCI [REDACTED]

[REDACTED]

[REDACTED]

[REDACTED]

[REDACTED]

[REDACTED]

[REDACTED]

[REDACTED]

Calculations of endpoints analysed by statistical models

Calculation of changes from baseline AUC (0-4)

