4.15 Changes in the Conduct of the Study or Planned Analysis

The following changes to the statistical methodology planned in Study Protocol will be applied:

- The repeated measures mixed model will also include the time term.

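### The SAP's TNF-alpha ANOVA leaves out period and has no defined dependent variable, because the protocol's TNF-alpha AUC was dropped without being declared as a change

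*SAP*

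**What the plan says.** **Model.** SAP section 4.12.2, under TNF-alpha concentrations: "An ANOVA model with treatment, sequence and subject as random effect will be run separately for each cohort (Cohort 1 and Cohort 2"), for the comparison at Day 3. The same section specifies the primary endpoint model "with treatment, period and sequence as fixed effects, participant within sequence as random effect and baseline as covariate". The endpoints analysed like the primary, and the CGM models, also include period.

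**Outcome.** Protocol section 9.4.2.2 says that for the TNF-alpha profiles "the AUC will be estimated and the measurements at the sampling points will be summarised", and continues: "Descriptive statistics will be tabulated both for the AUC and individual measurement points and treatments comparison will be conducted with ANOVA". The SAP keeps only the second half: "Descriptive statistics will be tabulated for the individual measurement points" of the LPS-stimulated levels. It defines no TNF-alpha AUC. Its pharmacodynamic AUC rules cover only the analytes of the mixed meal test.

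**Sampling.** The Schedule of Activities (Protocol section 1.3) takes a pre-dose sample and "Post-dose 1, 2, 4, 8, 12, 24 hours" on Day 3 of each period, study Days 3 and 30.

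**Declared changes.** SAP section 4.15 lists one change from the protocol: "The repeated measures mixed model will also include the time term".

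**The concern.** In a two-period crossover, sequence is a between-participant term and cannot absorb a shift between the two visits. If period is left out, the shift goes into the residual and, when the sequences are unequal in size, into the treatment contrast as well. TNF-alpha has less protection here than the other modelled endpoints. It is sampled only on Day 3, so even its pre-dose sample follows two doses, and its model has no untreated same-period baseline as covariate. The two sampling days are 27 days apart as scheduled (30 − 3), or more if washout is extended.

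The second problem is that the SAP does not say what the ANOVA is fitted to. Once the AUC is gone, seven values per profile remain with no time term, and the choice among them would be made at programming.

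The endpoint bears on the interpretation of the trial. Protocol section 4.3 treats equal anti-inflammatory effect as a precondition for a meaningful glucose comparison. It takes the dose pairing from this same biomarker in earlier studies: "40 mg prednisolone was predicted to be equipotent to 72 mg AZD9567", with a 95% CI of 52 to 99 mg.

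**Working it through.** The visible text gives no TNF-alpha sample size, SD, margin or power, so there is no plan figure to reproduce. The Cohort 1 size of 24 is set on glucose.

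**Inputs**
- Completers planned per sequence: 12/12 in Cohort 1 and 4/4 in Cohort 2 (Protocol section 4.1).
- Model terms: treatment and sequence read as fixed, subject as random (SAP section 4.12.2).
- Period shift π (period 1 minus period 2) and SD of the within-participant difference, SDd: not in the documents. I assume π between 0 and 1 SDd.

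**Step 1: what the model estimates.** Let τ be the effect of A minus B. The within-participant difference A − B has mean τ + π in sequence AB and τ − π in sequence BA. With complete pairs and no period term, the treatment estimate is the plain mean of these differences, so

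bias = π × (nAB − nBA) / N.

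With period in the model the bias is 0 at any split.

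**Step 2: planned balance.** At 12/12 and 4/4 the bias is 0 and the estimate is the same with or without period. The reported variance, however, is built from SDd² + π² × N/(N − 1) instead of SDd². Hence

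SE ratio = √(1 + (π/SDd)² × N/(N − 1)).

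| π / SDd | Cohort 1, N = 24 | Cohort 2, N = 8 |
|---|---|---|
| 0.25 | √(1 + 0.0625 × 24/23) = 1.032 | √(1 + 0.0625 × 8/7) = 1.035 |
| 0.5 | √(1 + 0.25 × 24/23) = 1.123 | √(1 + 0.25 × 8/7) = 1.134 |
| 1 | √(1 + 24/23) = 1.430 | √(1 + 8/7) = 1.464 |

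Without the N/(N − 1) factor the three values are 1.031, 1.118 and 1.414.

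A simulation of 40,000 trials per scenario, scaled to the within-participant SD (SDd = √2 times that SD), agrees. At 12/12 and a two-sided 5% level:
- Shift of 0.5 within-participant SD (0.35 SDd): type I error 3.9%. Power is about 77%, for an effect that has 80% power with period in the model.
- Shift of 1 within-participant SD (0.71 SDd): type I error 1.7% and power about 65%.

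**Step 3: unequal sequences, complete pairs**
- 13/11: 2/24 = 0.083π
- 14/10: 4/24 = 0.167π
- 4/3: 1/7 = 0.143π
- 5/3: 2/8 = 0.25π

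Participants with one period only matter less. Three such dropouts in one sequence on top of full balance give about 0.01π to 0.03π at 12/12 and 0.03π to 0.06π at 4/4. This takes the between-participant variance as 1 to 3 times the within-participant variance, which is an assumption.

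**Step 4: the undefined outcome.** The text allows two readings:
- Seven separate ANOVAs. The chance of at least one false positive per cohort is up to 1 − 0.95⁷ = 30.2% if the tests were independent, and lower because they are correlated.
- One pooled ANOVA on up to 7 × 2 = 14 values per participant. It has no time term, so the course over the day is not modelled. The section's general covariance rule does not say how these 14 values would be indexed.

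**The case against.** Several points on the other side stand.

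- A reader might infer that the TNF-alpha comparison is biased as planned. It is not: both cohorts are planned balanced by completers, withdrawals are to be replaced in Cohort 1, and at balance the bias is exactly 0. The reported SE widens and the test is conservative, so no false difference is created.
- A reader might infer that omitting period breaks the protocol. Protocol section 9.4.2.2 names ANOVA without listing its terms, so the omission is an inconsistency within the SAP. Nor does the protocol state outright that the ANOVA is run on the AUC; it says the AUC is estimated and tabulated and then mentions ANOVA. Only the loss of the AUC is an undeclared change.
- A reader might call this the trial's only check of equal anti-inflammatory effect. The documents do not say so. The stated objective is to explore AZD9567 exposure against TNF-alpha inhibition, which the planned scatter plot addresses. hsCRP is measured as a safety variable, and the exploratory objectives are redacted. With no margin set, a non-significant ANOVA could not show equality even with period included.
- With no period shift, omitting period is slightly better because it saves a degree of freedom: simulated power at 4/4 was 81.7% without period and 79.5% with it.

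None of this explains why TNF-alpha alone lacks period among the visible models, or says what the ANOVA is fitted to.

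**Conclusion.** The point holds as a matter of specification and consistency on a secondary endpoint. The SAP omits period from this one crossover model, drops the protocol's TNF-alpha AUC without declaring it, and leaves the dependent variable open across seven sampling times.

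At the planned balance the cost is an inflated reported SE, about 3% at a shift of 0.25 SDd and 12% to 13% at 0.5 SDd. If the sequences end unequal among complete pairs, the bias is the shift times the imbalance fraction, one seventh at 4 versus 3. The shift itself is assumed, and the documents give no basis for its size. Cohort 2, with four per sequence and no formal power, is where the loss of one participant matters most.

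A reader might also infer that the primary result is in doubt. It is not: the primary glucose model includes period. What suffers is the precision and clarity of a result that helps to judge whether the paired doses were comparable.

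**What to change.** In SAP section 4.12.2:
1. Make the Day 3 TNF-alpha AUC the named dependent variable. State its interval (the samples support 0 to 24 hours), its scale (the SAP already plots TNF-alpha on a log axis) and a missing-sample rule.
2. Fit treatment, period and sequence as fixed effects with participant within sequence as random, separately for Cohorts 1 and 2.
3. Report the treatment contrast with its 95% CI for each cohort, and keep the individual time points descriptive.

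If the AUC was dropped on purpose, declare and justify that in SAP section 4.15 and name the outcome that replaces it.

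The cost is one error degree of freedom per cohort (23 to 22 in Cohort 1, 7 to 6 in Cohort 2 at the planned numbers) and a short SAP edit. The edit includes new AUC rules for TNF-alpha, because the existing ones cover only the meal-test analytes. No further samples are needed.

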4.12.3 Pharmacokinetics

4.12.3.1 Concentrations

Plasma concentrations of AZD9567 will be listed by actual and relative (to dose administration) sampling time. The following summary statistics will be presented for these concentrations at each time point by treatment and cohort:

- n below the lower limit of quantification (LLOQ) (only for concentrations)
- Geometric Mean
- Geometric CV%
- Geometric Mean - SD
- Geometric Mean + SD
- Arithmetic Mean
- Arithmetic SD
- Median
- Minimum
- Maximum

In listings, concentrations less than the lower limit of quantification (LLOQ) will be presented as below the lower limit of quantification (BLQ). In listings and tables where the terms BLQ or LLOQ are included, the LLOQ (numerical value) will be included in a footnote.

For the calculation of statistics, concentrations that are BLQ will be handled as follows at each time point:

- If $\leq 50\%$ of the concentrations are BLQ, all BLQ values will be set to the LLOQ, and all descriptive statistics will be calculated.
- If $> 50\%$, but not all, of the concentrations are BLQ, the arithmetic mean, arithmetic CV, arithmetic mean, and arithmetic SD will be reported as 'NC' (not calculable). The maximum value will be reported from the individual data, and the minimum and median will be set as 'BLQ'.
- If all concentrations are BLQ, no descriptive statistics will be calculated. 'NA' (not applicable) will be presented for geometric CV, and arithmetic SD, and 'BLQ' will be presented for geometric mean, arithmetic mean, median, minimum, and maximum.

For PK concentration and parameter data, if there are <3 values available at a time point, only the maximum, minimum, and n will be reported; the remaining descriptive statistics will be reported as 'NC'. Concentrations that are BLQ are considered a value.

Post-dose concentrations where the actual time deviation deviates more than 10% from the scheduled time will be excluded from summaries by planned time point.

Missing samples will be reported as no sample ("NS") and excluded from analysis.

Source data shall be used in all derived PK concentrations without prior rounding

The following figures, will be generated for each IMP by Cohort:

- Individual Subject Profiles, Plasma Concentration-time Data - Linear Scale: both days on 1 plot
- Individual Subject Profiles, Plasma Concentration-time Data - Semi-Logarithmic Scale : both days on 1 plot
- GMean, Plasma Concentration-time Data - Linear Scale: both days on 1 plot
- GMean, Plasma Concentration-time Data - Semi-Logarithmic Scale: both days on 1 plot.

In combined figures displaying subject profiles, all subjects will be included in the same figure and concentrations will be displayed by actual sampling time. In figures displaying mean concentrations, mean concentrations will be displayed by time point.

4.12.3.2 Pharmacokinetic Parameters

Pharmacokinetic parameters will be calculated following these guidelines:

Pharmacokinetic analysis will, where possible, be calculated using times recorded in the raw data. If actual times are missing, nominal times may be used.

The concentrations reported by the analytical laboratory for PK analysis will be used in all the analyses. The units of concentration and resulting PK parameters, with amount or concentration in the unit, will be presented as they are received from the analytical laboratory.

C_{max} and t_{max} will be obtained directly from the plasma concentration-time profiles. For multiple peaks, the highest post-dose concentration will be reported as C_{max}. In the case that multiple peaks are of equal magnitude, the earliest t_{max} will be reported.

Concentrations BLQ from the time of pre-dose sampling (t=0) up to the time of the first quantifiable concentration will be set to zero with the following exceptions:

- Any embedded BLQ value (between 2 quantifiable concentrations) and BLQ values following the last quantifiable concentration in a profile will be set to missing for the purposes of PK analysis.
- If there are late positive concentration values following 2 BLQ concentration values in the apparent terminal phase, these values will be set to missing, unless there is a scientific rationale not to do so, which will be documented by the pharmacokineticist.
- If an entire concentration-time profile is BLQ, the profile will be excluded from the PK analysis.
- If a pre-dose concentration is missing, these values may be set to zero by default.

The terminal elimination rate constant (λ_z) will be calculated by log-linear regression of the terminal portion of the concentration-time profile. The following will be considered:

- If more than one phase is present only data points from the terminal phase will be used.
- A minimum of 3 data points after C_{max}, including the last measurable concentration, will be used for calculating λ_z .
- Where the elimination half-life is estimated over less than 3 times the subsequently estimated terminal half-life the robustness of the $t_{1/2\lambda}$ estimate will be discussed in the CSR.
- R_{sq} adjusted should be greater than 0.8. Where R_{sq} adjusted < 0.8, half-life and half-life dependent parameters may be excluded from summary statistics and statistical analysis with sponsor agreement.

The AUCs will be calculated using the linear trapezoidal method when concentrations are increasing and the logarithmic trapezoidal rule when concentrations are decreasing (linear up log down). The minimum requirement for the calculation of AUC will be the inclusion of at least 3 consecutive plasma concentrations above the LLOQ.

Generally, data should not be excluded from analysis. However, where this is scientifically merited a sensitivity analysis may be performed and the data will be discussed in the CSR.

Pharmacokinetic summaries will be based upon the PKAS.

Pharmacokinetic parameters will be listed by subject and summarised by treatment. Descriptive statistics for calculated PK parameters will include: n, arithmetic mean, SD, CV%, geometric mean, geometric CV%, median, minimum and maximum values. For tmax, only median, minimum and maximum values will be presented. No descriptive statistics will be determined when fewer than three individual PK parameters are available.

The following rules will be followed with regards to the number of decimal places and presentation of data in the tables and listings for PK parameters:

- Individual PK parameters will be presented to four significant digits, with the exception of tmax, which will be presented to two decimal places.
- Parameters derived directly from source data (e.g. Cmax,) shall be reported with the same precision as the source data (if this is not four significant digits).
- The mean, geometric mean, median and SD values will be reported to four significant digits, all other descriptive statistics will be reported to three significant digits except for CV% which will be presented to one decimal place.
- For tmax the minimum and maximum will be presented to two decimals places and all other descriptive statistics will be presented to three decimal places.

